### 3.1.b. Phase 2: Screening Only (SO) vs. SUSIT

Phase 2 is conducted at Bellevue Hospital's Adult Primary Care Clinic and Virology Clinic. Adult patients of the participating PCPs will be recruited and enrolled following the procedures detailed in Section 5. The participating PCPs will receive screening results, CDS, and clinical reminders during the SUSIT condition, to help them address unhealthy drug use in their patients. The intervention that patients receive is determined by the period in which they are enrolled (i.e. Screening Only (SO)

vs. SUSIT), as indicated in Figure 3. Participating patients in both the SO and the SUSIT condition will enter responses to the tablet computer self-administered substance use screening tool. Screening is self-administered using a touch-screen tablet, and completed by patients in the waiting area prior to the clinical encounter. Substance use screening is part of a brief 'healthy lifestyle survey,' which also includes items on diet and exercise adapted from an existing health risk assessment. After the baseline medical encounter, patients will provide verbal responses to structured interviews. They will also complete a demographics form, and a self-administered computerized exit survey to ascertain whether their PCP provided elements of a substance use brief intervention during the medical visit, and various assessments described below. The exit survey will be administered again at any follow-up medical visits with the PCP that occur during the study period.

Figure 3. Study conditions

**Screening Only (SO) condition:** Patient and PCP are not presented with screening results. The PCP does not receive clinical decision support, or clinical reminders.

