In both the SO and SUSIT conditions, study visits are at baseline (same day as the primary care visit), 3 months, and 6 months. Exit surveys ascertain what elements of brief intervention were conducted by the PCP, and are conducted at the baseline visit, the 3 month, the 6 month and at each follow-up medical visit. If the patient has not seen their provider in the last 3 months, they will not have to complete the survey. To minimize any potential for the RA to influence reporting, patients will self-administer the exit survey, prior to collection of additional substance use measures. PCPs will receive a clinical reminder for patients in the SUSIT condition, and may consequently address substance use differently than in the SO condition. For this reason, we will record scheduled follow-up medical appointments, and call, email or text participants several days prior to appointments.

At the baseline study visit, and at the 3- and 6-month study visits, the RA will administer substance use assessments: Timeline follow-back (TLFB), Composite International Diagnostic Interview, Second Edition, Substance Abuse Module (CIDI-SAM), for Spanish speaking patients the M.I.N.I (Mini-International Neuropsychiatric Interview) will be used as the measure of substance use disorder, because the CIDI is not currently available in Spanish, the Short Inventory of Problems for alcohol and drugs (SIP and SIP-DU), the first 8 items of the Patient Health Questionnaire (PHQ-8), and the Generalized Anxiety Disorder 7-item scale (GAD-7). Participants will provide hair samples for drug toxicology testing at the month-6 study visit. This will detect common drugs of abuse, as a means of corroborating self-report of recent drug use. If after repeated outreach attempts, and the participant is still not able to meet with RA in person, a phone interview will be scheduled with the participant for either the 3 or 6 month follow-up interview. This will be a one-to-one phone interview, with the RA or RC (whomever is conducting the interview) will be a private area. When scheduling the phone interview will ask the participant to ensure being in private space during the phone interview. For those participants that will have their 6 month interview by phone, the hair sample will become not applicable for those participants.

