Chart review: Research staff will perform a structured chart review of the participant's medical record that examines the content of notes written by the participant's primary care provider(s) during the 12 months following study enrollment (inclusive of the date of enrollment). The chart review collects similar information to the patient exit survey; namely, documentation of any discussion by the primary care provider about drug, tobacco, or alcohol use. The chart abstraction form will be approved by the IRB.

Individual in-depth interviews with patient participants will characterize the acceptability to patients of conducting substance use screening and interventions in primary care. A purposive sampling approach will be used to select 12 patients who are already enrolled in the SO or SUSIT arm of the study. Those selected will represent a range of sex and age groups. The attitudes of patients are particularly important when addressing a stigmatized behavior such as substance use. While self-administered screening tools may allow for more honest reporting of stigmatizing behaviors, some patients might prefer face-to-face communication with their providers.

Table 1. Phase 2 Outcomes and measures

Outcome	Measures	Source	Collected at
Primary Outcome:			

Patient receipt of a substance use intervention	Audio recordings of medical visits, transcribed and coded with BAS scale	Audio recording of medical visit	Baseline and all follow-up PCP visits (SUSIT condition only)
	Patient exit survey: -Frequency of intervention -Elements of intervention	Patient (self-administered)	Baseline and all follow-up PCP visits
	Chart review -Frequency of intervention -Elements of intervention	Medical Record	Baseline and all follow-up PCP visits
Secondary Outcomes:			
Disclosure of substance use on screening	ACASIASSIST vs. TLFB and hair test results	Patient	Baseline 3- and 6-month study visit*
Self-reported drug and alcohol use	90-day TLFB	Patient	Baseline 3- and 6-month study visits
Drug or alcohol use severity	CIDI-SAM	Patient	Baseline 3- and 6-month study visits
Problems related to drug or alcohol use	SIP, SIP-D	Patient	Baseline 3- and 6-month study visits
Psychological well-being	GAD-7, PHQ-8	Patient	Baseline 3- and 6-month study visits
Biologic measure of any drug use	Hair testing	Lab result	6-month study visit*
Acceptability to patients of screening and interventions	In-depth interviews	Patient	Individual interviews with 6 patients in each study period

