\* Hair testing will become not applicable for any patient participant that completes 6 month interview over the phone

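### Does the plan need to state which ASSIST, TLFB and hair time points are paired for the screening-disclosure outcome?

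*Combined protocol and SAP*

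**What the plan says.** Table 1 of section 3.1.b lists the disclosure outcome with the measures "ACASIASSIST vs. TLFB and hair test results" and the timing "Baseline 3- and 6-month study visit", followed by an asterisk. The asterisk leads to a footnote about hair only: "Hair testing will become not applicable for any patient participant that completes 6 month interview over the phone". Hair also has its own row in Table 1, timed at the 6-month visit alone.

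The text of section 3.1.b places the tablet screen before the baseline medical visit, "completed by patients in the waiting area prior to the clinical encounter". Section 5.1 describes the same screen as the eligibility step. For study visits at baseline, 3 and 6 months, section 3.1.b lists what the research assistant administers: the TLFB, a diagnostic interview, the problem inventories, and the depression and anxiety scales. The ASSIST is not in that list. On order of administration it says "patients will self-administer the exit survey, prior to collection of additional substance use measures". On hair it says "Participants will provide hair samples for drug toxicology testing at the month-6 study visit", and gives the purpose "as a means of corroborating self-report of recent drug use".

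Section 3.2.a sets out a model for the primary outcome and none for this comparison. Section 4.2 names the TLFB as the main Aim 3 measure and says it can be done by phone.

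**The concern.** An outcome that compares instruments is not fully defined until the pairs are named, and here they are not. The one timing entry covers three measures, although hair is never taken at baseline or month 3, so the entry cannot show by itself which measure is taken when. Read with the prose, which describes only a baseline screen, the row could be taken to set a baseline ASSIST against a hair sample cut six months later.

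The study hopes to reduce drug use between those two dates. Under that reading, real change in use would be counted together with misreporting on the screen. With no written rule, the pairing could also be chosen after the data are seen.

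**Working it through.** The plan attaches no sample size, power or error rate to this outcome, so there is no figure to reproduce. The check is of time windows and of the direction of any error.

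**Inputs from the documents**
- Screen: use in the past 3 months (section 2.2), taken at baseline.
- TLFB: 90 days (Table 1), at baseline, 3 and 6 months.
- Hair: 1.5 inches of head hair (section 4.2), at month 6.

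**Input assumed**
- Hair growth of 0.3 to 0.6 inch a month. The documents give no growth rate.

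**Windows, in months from baseline, visits on time**

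| Measure | Window | Overlap with baseline screen (−3 to 0) |
|---|---|---|
| Baseline TLFB | −3 to 0 | 3 |
| Month-3 TLFB | 0 to 3 | 0 |
| Month-6 TLFB | 3 to 6 | 0 |
| Hair, growth 0.3 | 1.5/0.3 = 5.0 months back: 1.0 to 6 | 0 |
| Hair, growth 0.6 | 1.5/0.6 = 2.5 months back: 3.5 to 6 | 0 |

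The sample would reach back past baseline only if growth were below 1.5/6 = 0.25 inch a month. Against the month-6 TLFB (3 to 6), the same sample overlaps by 3.0 months at growth 0.3 and 2.5 months at growth 0.6. Section 4.2 also allows body hair, whose look-back is not stated. An early visit changes little: a month-3 visit on day 77 (an assumed target of day 91, less 14 days) gives a TLFB window from day −13 to day 77, which shares 13 of the screen's 90 days.

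So a baseline screen matches the baseline TLFB, and month-6 hair matches month-6 self-report. Crossing the two sets would be a poor comparison.

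**Does the plan cross them?** No sentence says so. Three features point the other way:
1. The disclosure row lists the same three visits as the TLFB row, which reads most naturally as comparison visit by visit.
2. Hair is given the role of corroborating recent self-report, and at month 6 that is month-6 self-report.
3. The list that omits the ASSIST is of measures the research assistant administers. The ASSIST is self-administered, so its absence there is weak evidence that it is not repeated.

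**Which way would an error run?** Every enrolled patient screened positive for at least one drug (sections 2.2 and 5.1).

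| Baseline screen | Later measure | What happened | How it would look |
|---|---|---|---|
| Positive | Negative | Use stopped | Discordance, or apparent over-report |
| Negative for that substance | Positive | New use began | Apparent non-disclosure |

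The change the study hopes for falls in the first row. It would not be scored as a failure to disclose. Only new use of a substance denied at baseline would be.

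**The case for a change.** The strongest case for acting is that the fix is cheap and the gap is real on either reading. If the ASSIST is not repeated, Table 1 lists visits at which one side of the comparison does not exist. If it is repeated, section 3.1.b does not describe it, and nothing says how a touch-screen questionnaire is completed when a follow-up visit is by phone. Lost spacing in the table does not explain this, because the prose supports the point independently. Section 4.3.c adds that follow-up reminders to the provider carry the baseline screening result.

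Much of this stands. The documents do not settle whether the ASSIST is repeated, and the pairing is unwritten. The reminder wording counts for less, since it concerns what the provider receives and not what research staff collect. Silence in section 3.2.a is not particular to this outcome either: no secondary outcome in Table 1 has a quantitative model there.

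A stricter rule would also have a price. If the ASSIST is not repeated, allowing only measures of the same period removes hair, the sole biological comparator, and leaves one self-report checked against another. That second report is collected after staff can see the screening scores and, in the SUSIT condition, after the patient has been shown them, so agreement could look too good. A descriptive comparison with hair, its timing limit stated, is a reasonable alternative. Choosing between the two is a matter of judgement.

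**Conclusion.** The gap exists, but it does not call for a change. It is an unwritten pairing rule for one minor secondary outcome in a study that describes its efficacy evidence as preliminary. The mismatch would be complete if someone paired the baseline screen with follow-up measures (0 months of overlap with visits on time), but the plan does not ask for that. Its visit list and the stated purpose of the hair test lead an analyst to same-visit pairs: baseline ASSIST with baseline TLFB, any repeated ASSIST with the TLFB of the same visit, and month-6 hair with month-6 self-report.

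The primary outcome and the main Aim 3 measure are unaffected. The conclusion assumes that analysts pair like with like and, if the ASSIST was taken only once, that any comparison with hair is reported as descriptive with its timing stated. The zero overlap for head hair holds across the assumed growth range of 0.3 to 0.6 inch a month; nothing can be said about body hair.

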#### PCP assessments in Phase 2, SO and SUSIT conditions:

PCP focus groups: All participating PCPs will be invited to participate in focus groups, which occur prior to the SO period, and again 3 months following implementation of the SUSIT. Focus groups will be conducted by the PI to assess the provider-level factors that are anticipated to have the greatest impact on adoption. In the focus group conducted during the SUSIT period, themes will be explored in the context of their experience with the SUSIT.

Substance abuse attitudes survey: Provider attitudes can influence delivery of SBI to patients. Because PCPs may be reluctant to share negative attitudes toward substance use and users in a focus group, we will use the validated Substance Abuse Attitudes Survey (SAAS) to measure subjective norms. Because PCP attitudes may change in response to increased experience addressing substance use in their patients, the SAAS and modified TAM2 questionnaire will also be given at the end of the SUSIT period.

### **3.2. Data analysis and data monitoring**

#### 3.2.a. Data analysis

##### Qualitative data analysis (Phases 1 and 2):

In-depth interviews and focus groups (conducted in Phases 1 and 2) will be audio taped and transcribed, then coded using Atlas.ti. We will use an a priori coding scheme based on themes related to the TAM2 model elements, and additionally identify any concepts relevant to adoption of the SUSIT that were not included in the a priori list (i.e. emergent themes) using a grounded theory approach. Analysis will be conducted by a 3-person team of [name], [name], and the Research Coordinator (RC). Initial coding of the transcripts will be done by the RC using a coding guide jointly developed by the analysis team. The coding schemes will be continually compared for consistency. The investigators will independently read and analyze the transcribed sessions, then discuss the findings until a consensus is reached on the core categories and main findings.

Audio recordings of medical encounters (conducted in Phase 2, SUSIT condition) will be reviewed and coded by the Research Coordinator using the validated Brief Intervention Adherence Scale (BAS). The BAS is a 21-item checklist developed for the purpose of assessing the content of brief intervention delivered by health care providers, and has been used as a fidelity measure in alcohol SBI trials.

#### Quantitative data analysis (Phase 2):

The data structure follows a hierarchy of patient-level data nested within providers, during the SO vs. SUSIT study period. For analysis of the primary outcome, which is measured at the patient level, we will first examine whether any brief intervention occurred, in at least one visit, during the study period. For additional descriptive information we will count the number of visits in which an intervention occurred, and the number of elements of the brief negotiated interview documented in each visit. The “receipt of brief intervention” outcome analyses will use a generalized linear mixed model (i.e., multilevel logistic regression) with a random intercept and patients nested within primary care providers. The key explanatory variable will be treatment condition (SUSIT vs. SO). When the fixed effect of treatment condition is exponentiated, this coefficient indicates how the odds of receiving brief intervention are multiplied when an individual receives the SUSIT condition rather than screening only. Patient-level and PCP-level covariates (e.g., substances used, provider SAAS score) can be added to the multilevel logistic regression analysis if they are significantly related to the odds of intervention. Any patient-level covariates will be grand mean centered following our focus on treatment condition effects.

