### 1.3. Study design

The proposed study will develop (in Phase 1) a clinical decision support tool that assists primary care providers in carrying out substance use interventions, and then compare (in Phase 2) two

PROTOCOL

s16-01074

[figure not shown]
clinical scenarios, screening only (SO) vs. SUSIT, on dose of substance use brief intervention

Version 8.6

01/22/2019

received, and changes in drug use at 3 and 6 months, among primary care patients. We will develop the CDS component and then test the full SUSIT approach, using mixed methods to assess its acceptability and adoption, and gathering preliminary data on its efficacy for reducing unhealthy drug use. CDS development is concurrent with the SO phase to avoid losing valuable time, but will be conducted at a secondary study site to avoid contaminating the SO condition. In each treatment condition we will enroll 75 patients with moderate-risk drug use, who present for a medical visit with one of ten PCPs (Figure 1). A pre-post design will ascertain the dose of substance use intervention received and changes in drug use among patients enrolled in the screening only (SO) versus SUSIT intervention period.

Figure 1: Study design

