## **2.2. Inclusion and exclusion criteria**

Primary Care Providers: Up to 65 PCPs are anticipated to participate in the study. In Phase 1, up to 35 PCPs from Gouverneur Health and Bellevue will participate in content development, usability testing and clinical testing of the clinical decision support tool. In Phase 2, up to 30 PCPs from Bellevue Hospital will participate. Participating PCPs can be medical doctors (MDs), doctors of osteopathic medicine (DOs), nurse practitioners (NPs), or physician assistants (PAs). Medical students and residents are not included. There are no additional eligibility or exclusion criteria for providers.

**Patients:** Up to 200 patients are anticipated to participate (50 in Phase 1, and 150 in Phase 2). Patients are recruited if they have a medical visit with one of the participating PCPs. Because the SUSIT self-administered screening instrument is currently available in English and Spanish, the study is restricted to English and Spanish speaking patients.

Inclusion criteria:

- Substance use screening results (collected using the tablet-based screening tool) indicating current moderate risk drug use, based on a substance specific involvement score (SSIS) indicating current (past 3 months) use of at least one drug with a moderate risk level (SSIS 4-26), in the absence of any high-risk drug or alcohol use (SSIS 27+);
- 18 years or older;
- English and Spanish speaking;
- Presenting for visit with a participating PCP; and
- Able to provide informed consent
- Available to complete two follow up visits (3 months and 6 months after baseline appointment)

Exclusion criteria:

- Prior participation in the study (i.e. participation in the SO study phase would preclude participation in the SUSIT phase);
- Attending a formal addiction treatment program (not including informal treatment such as Alcoholics Anonymous, Narcotics Anonymous), in the past 3 months;
- Pregnant (based on self-report).
- Unable to read text on the tablet-based screening tool, or physically unable to operate the tablet.

The PI's prior study in this clinic indicates that 17% of all patients will meet eligibility criteria.

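### SO patients' follow-up visits can fall after their own PCP has begun SUSIT, and the primary outcome has no rule that keeps them out

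*Combined protocol and SAP*

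**What the plan says.** **Allocation.** Section 3.1.b says: "The intervention that patients receive is determined by the period in which they are enrolled". Section 1.3 says: "In each treatment condition we will enroll 75 patients with moderate-risk drug use, who present for a medical visit with one of ten PCPs". Section 2.2 gives a different PCP count, "In Phase 2, up to 30 PCPs from Bellevue Hospital will participate", but this point does not depend on which is right.

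**Order of the periods and shared PCPs.** All participating PCPs are invited to focus groups "which occur prior to the SO period, and again 3 months following implementation of the SUSIT" (PCP assessments in Phase 2). Section 3.1.b adds: "The participating PCPs will receive screening results, CDS, and clinical reminders during the SUSIT condition". For SO patients the PCP gets none of these.

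**Outcome.** Section 3.2.a scores a patient as positive if any brief intervention took place "in at least one visit, during the study period". Table 1 takes exit-survey and chart-review data from the baseline visit and every later PCP visit. Study visits end at 6 months. Chart review covers provider notes "during the 12 months following study enrollment (inclusive of the date of enrollment", and section 5.2 extends it to patients already enrolled in SO.

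**Safeguards.** Section 1.3 says: "CDS development is concurrent with the SO phase to avoid losing valuable time". It places that work at a secondary site so as not to contaminate SO. Section 2.2 bars a patient from entering both phases. Neither provision concerns SO patients' visits after the switch.

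**The concern.** With an any-visit outcome, a single late visit can turn an SO patient from negative to positive. If the PCP has by then been using SUSIT with other patients, that visit may reflect SUSIT-influenced practice although it is counted under SO. The protocol treats this mechanism as plausible. It says that provider attitudes affect delivery and may shift as PCPs gain experience, and it takes steps against contamination during CDS development.

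At stake is the primary comparison. Spill-over would raise the SO rate, pull the odds ratio toward 1 and cost power. The planned model contains condition, a PCP random intercept and optional covariates. None of these terms records whether a given SO visit came before or after that PCP began SUSIT.

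**Working it through.** The plan gives 75 patients per condition. It gives no event rates, alpha, power, accrual time or gap, so there is no planned figure to reproduce. What follows is an illustration.

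**Step 1: how much SO follow-up could fall after the switch**

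Inputs from the plan: outcome window W = 6 months (study visits) or 12 months (chart review). Assumptions: SO enrolment is uniform over T = 6 to 18 months, and there is a gap g between the last SO enrolment and SUSIT start.

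- Share of SO patients with some window after the switch = min(1, max(0, (W − g)/T)).
- Share of total window after the switch, with g = 0: W/(2T) if T ≥ W, otherwise 1 − T/(2W).

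| W | T | Patients with any overlap, g = 0 | Window after switch, g = 0 | Patients with any overlap, g = 6 |
|---|---|---|---|---|
| 6 | 6 | 100% | 6/12 = 50% | 0% |
| 6 | 12 | 50% | 6/24 = 25% | 0% |
| 6 | 18 | 33% | 6/36 = 17% | 0% |
| 12 | 6 | 100% | 1 − 6/24 = 75% | 100% |
| 12 | 12 | 100% | 12/24 = 50% | 50% |
| 12 | 18 | 67% | 12/36 = 33% | 33% |

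A 6-month gap clears the study-visit window. Chart review needs 12 months.

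**Step 2: effect on the primary comparison**

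Assumptions: three visits per patient; per-visit intervention probability 20% in SO and 45% in SUSIT; 30% or 40% at an SO follow-up visit after the switch; visits independent; no PCP clustering; two-sided 5% test.

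- SUSIT, any visit: 1 − 0.55³ = 0.834, odds 5.01.
- SO, any visit: 1 − 0.8 × (1 − c′)², where c′ = 0.20 + e × (c − 0.20), e is the share of follow-up visits after the switch, and c is 0.30 or 0.40.
- Power = Φ((d − 1.96 s₀)/s₁), where d is the difference in proportions, and s₀ and s₁ are its pooled and unpooled standard errors with 75 per group.

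| e | c | c′ | SO, any visit | OR | Power |
|---|---|---|---|---|---|
| 0 | – | 0.200 | 0.488 | 5.26 | over 99% |
| 17% | 0.30 | 0.217 | 0.509 | 4.83 | 99% |
| 17% | 0.40 | 0.233 | 0.530 | 4.45 | 98% |
| 50% | 0.30 | 0.250 | 0.550 | 4.10 | 97% |
| 50% | 0.40 | 0.300 | 0.608 | 3.23 | 88% |

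The 6-month window with no gap gives e between 17% and 50%, hence an OR between 4.8 and 3.2. With the 12-month shares from Step 1 (33% to 75%) and still three visits, the OR runs from 4.45 to 2.56 and power from 98% to 68%.

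As a check on spreading exposure evenly over visits, suppose instead that half of SO patients have both follow-up visits after the switch and half have none. The SO rate is then (0.488 + 0.608)/2 = 0.548 to (0.488 + 0.712)/2 = 0.600. The OR is 4.13 to 3.34 and power 97% to 90%, much the same.

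**Step 3: the other reading of the study period**

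Sections 3.1.b and 4.3.c use the term for a patient's own follow-up. Section 1 and the last row of Table 1 use it for the SO or SUSIT calendar period, and section 3.2.a opens its paragraph in that sense. On the calendar reading, visits after the switch drop out, but late SO enrolees then have less time in which to score a positive visit. At 20% per visit, one visit gives 20% and three give 49%. This is a different bias. Its direction depends on whether late SUSIT enrolees are cut short in the same way, which the text does not say.

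**The case against.** The strongest reply is that overlap is not shown. No dates, accrual times or gap are given, and Figures 1 and 3 are not available in the text. Developing the CDS alongside SO does not mean that SUSIT starts the day SO enrolment ends. If the periods are far enough apart, no rule is needed. This stands. A reader might infer that the SO condition is contaminated, but the documents support only that it can be.

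The route is also indirect. For SO patients the PCP receives no results, CDS or reminders, and the SUSIT materials are specific to the patient. Spill-over would need a general change of habit. This stands too, and the documents give no basis for its size.

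A reader might push the assumed rates further and infer that power falls to 43% (SO 71%, OR 2.0). That needs every SO follow-up visit to fall after the switch, and a post-switch rate of 40%, which is (40 − 20)/(45 − 20) = 80% of the assumed SUSIT effect. Nothing in the documents supports that combination.

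Nor do all PCPs cross over. The enrolment-only sites join only the SUSIT condition, so their PCPs have no SO patients.

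Finally, the bias runs toward no effect, so it would not by itself explain away a positive result. That is correct. It still matters for a null result and for the size of the estimate.

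The reply does not supply a definition of the study period or a rule on which SO visits count.

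**Conclusion.** The concern holds in conditional form. On the per-patient reading, SO visits after the PCP's switch would count toward the primary outcome, and nothing in the text prevents this. On the calendar reading they would not count, but SO follow-up becomes unequal. Each reading leaves a problem that a defined window would remove.

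Under the assumed rates, with a 6-month window, no gap and accrual of 18 to 6 months, the OR moves from 5.3 to between 4.8 and 3.2, and power from over 99% to between 99% and 88%. These figures rest wholly on assumed rates, visit counts, accrual and spill-over, and they ignore clustering by PCP. The 12-month chart window is more exposed than the 6-month window. If SUSIT began at least 12 months after the last SO enrolment, neither window overlaps.

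**What to change.** 1. Define the primary outcome over one fixed window per patient, counted from enrolment. It should be the same in both conditions and for both exit survey and chart review.
2. Exclude SO visits and notes dated on or after the day that patient's PCP started SUSIT. If the PCP has no SUSIT patient, use the clinic's start date.
3. Truncate the SUSIT windows to match, by a rule written before the data are analysed. Without this step, shortened SO follow-up on an any-visit outcome would favour SUSIT.
4. State the start and end dates of both periods and any gap between them.
5. Add a sensitivity analysis on the index visit alone. For SO patients this visit precedes SUSIT rollout. It should not be described as fully protected, because Bellevue PCPs take part in the Phase 1 CDS interviews and usability testing, and CDS development runs alongside SO.

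The cost is an added outcome rule using enrolment, visit and chart-note dates, which should be available from study records. Some later visits leave the primary analysis, with some loss of information. If the gap covers the full window, no SO visits are lost.
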